9.2.2 Patient-Reported Outcomes

9.2.2.1 Primary Endpoint

- Change in FACT/GOG-Ntx TOI score calculated as the difference after completion of 12 cycles of study therapy from baseline
- Change in FACT-MM TOI score calculated as the difference after completion of 24 cycles of study therapy from baseline

9.2.2.2 Secondary Endpoints

- Levels and changes from baseline of all instruments
- Time to worsening of FACT/GOG-Ntx TOI defined as the time from baseline to a decrease of 8 points (MID), respectively, or censored at the date of last assessment
- FACT/GOG-Ntx TOI recovery rate in the patients experiencing a MID decrease, the proportion of patients with the FACT/GOG-Ntx TOI score returning to baseline level
- Time to improvement of the FACT-MM TOI defined as the time from baseline to an increase of 10 points (MID), respectively, or censored at the date of last assessment
- FACT-MM TOI response rate defined as the proportion of patients experiencing a MID improvement since baseline at each assessment time point

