6.3.2 Patient-Reported Outcomes Assessment Schedule

PRO time-points overlap with protocol-specified clinic visits. The NCI PRO-CTCAE will be assessed at baseline and the beginning of each cycle on study therapy up to two-years. The FACT-G (PWB+FWB), Ntx and MM are first administered at baseline prior to starting treatment for evaluation of change longitudinally. The FACT-G (PWB+FWB), Ntx and MM then will be administered every three cycles for the first 24 cycles (beginning of cycles 4, 7, 10, 13, 16, 19, 22 and 25) and every six cycles thereafter up to completion of 48 cycles (beginning of cycles 31, 37, 43, 49), and at treatment discontinuation prior to completing 48 cycles. During long-term follow-up, there will be 4 quarterly assessments for one year. The ASK-12 will be assessed every six cycles on treatment up to completion of 48 cycles (beginning of cycles 7, 13, 19, 25, 31, 37, 43, and 49).

Assessment Timepoint ^{1,2}		Questionnaires to be Administered		
Study Cycle	FACT-G, Ntx and MM ³	PRO-CTCAE	ASK-12	
Baseline				
Within 28 days prior to Step 1 registration	X	X		
On Treatment				
Cycles 2-3		X		
Cycle 4	X	X		
Cycles 5-6		X		
Cycle 7	X	X	X	
Cycles 8-9		X		
Cycle 10	X	X		
Cycles 11-12		X		
Cycle 13	X	X	X	

Assessment Timepoint ^{1,2}	Questionnaires to be Administered		
Study Cycle	FACT-G, Ntx and MM ³	PRO-CTCAE	ASK-12
Cycles 14-15		X	
Cycle 16	X	X	
Cycles 17-18		X	
Cycle 19	X	X	X
Cycles 20-21		X	
Cycle 22	X	X	
Cycles 23-24		X	
Cycle 25	X	X	X
Cycle 31	X		X
Cycle 37	X		X
Cycle 43	X		X
Cycle 49	X		X
Long Term Follow-Up⁴			
3 months post-tx	X		
6 months post-tx	X		
9 months post-tx	X		
1-year post-tx	X		

¹ +/- 7 days if appointments on the scheduled date are missed, the questionnaires will be mailed electronically to participants who will be asked to complete the questionnaires and return answers by electronic mail to the clinic. After 7 days, clinic or research staff may contact participants by telephone and ask participants to complete the questionnaire over the telephone reading their answers to the staff person. This approach will approximate the completion of PROs in clinic as closely as possible.

² Assessments to be completed at beginning of the cycle +/- 7 days.

³ FACT-G, Ntx and FACT-MM measures are included on one paper form. FACT-G, Ntx and MM will also be assessed at treatment discontinuation prior to 48 cycles

⁴ Months post-treatment with respect to the date of discontinuation of treatment.

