There are two key secondary health-related QOL analysis comparing treatment arms: Time to worsening of the FACT/GOG-Ntx TOI and time to improvement of the FACT-MM TOI. Time to worsening of the FACT/GOG-Ntx TOI and time to improvement of the FACT-MM TOI will be analyzed with the KM method and compared using the log-rank test. We will establish significance as alpha=1.67% based on Bonferroni adjustment (5% divided over 3 comparisons). We will provide rates on each arm including exact binomial 95% confidence intervals for the FACT/GOG-Ntx TOI recovery rate and FACT-MM TOI response rate.

As exploratory, correlation between time to worsening of symptoms with PFS and OS will be assessed with Kendall's Tau adjusted for censored observations.

Finally, we will evaluate whether patients with poor treatment adherence based on medication calendars and lower likelihood of medication adherence based on ASK-12 scores have lower QOL scores [the FACT/GOG-Ntx TOI, FACT-MM TOI and FACT-G (FWB and PWB subscales)] after 12- and 24-cycles of treatment. Linear regression analysis at these 2 time points separately will be conducted with QOL score as outcome and treatment adherence group as the main effect adjusting for baseline QOL score along with other disease and demographic characteristics.

PRO-CTCAE

Analyses related to the PRO-CTCAE are exploratory. Descriptive statistics will be used to summarize selected PRO-CTCAEs tabulated at each cycle overall and by arm. We will map PRO-CTCAEs with provider reported AEs and evaluate differences in incidence and worst severity. PRO-CTCAE ratings will further be evaluated in relation to patient bother by treatment side effects (FACT-GP5 item, "I am bothered by treatment side effects") to identify the toxicities that are most highly associated with treatment tolerability issues.

Medication Adherence Scale

Analyses related to the ASK-12 are exploratory. Descriptive statistics will be used to summarize ASK-12 scores tabulated every 6 cycles on study therapy. The ASK-12 is reported to have a mean (standard deviation) of 27.5 (7.2). Differences between arms will be evaluated

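### The FACT/GOG-Ntx TOI recovery rate has no time window and no rule for patients without a later form, so the arm rates depend on how long patients are observed after worsening

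*Combined protocol and SAP*

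**What the plan says.** Section 9.2.2.2 defines the endpoint, among patients whose score has fallen by the MID, as "the proportion of patients with the FACT/GOG-Ntx TOI score returning to baseline level". The drop that puts a patient in the denominator is 8 points. Section 9.3.4 gives the whole analysis: "We will provide rates on each arm including exact binomial 95% confidence intervals for the FACT/GOG-Ntx TOI recovery rate". No between-arm test of this rate is planned.

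The neighbouring endpoints in 9.2.2.2 are better specified. Time to worsening and time to improvement are both censored at the last assessment. The FACT-MM response rate is "the proportion of patients experiencing a MID improvement since baseline at each assessment time point". Recovery has neither a censoring rule nor a time point.

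Section 6.3.2 fixes when recovery can be seen. Forms come every three cycles to cycle 25, every six cycles to cycle 49, and "at treatment discontinuation prior to completing 48 cycles". After that: "During long-term follow-up, there will be 4 quarterly assessments for one year". Section 5.1.1 continues treatment until progression or unacceptable toxicity.

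**The concern.** A return to baseline is recorded only if a form is returned after the one that showed the drop. A patient with three years of later forms has many chances to be seen recovering. A patient whose drop appears on the last form has none. A crude proportion gives both the same weight, so each arm's rate mixes recovery with length of observation.

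Length of observation depends on treatment duration, which the trial drug can change in either direction. Delayed progression lengthens it and toxicity shortens it.

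Recovery is half of secondary PRO objective 2.4.2.1, and it bears on how lasting any ixazomib neuropathy is. Readers will set the two arm rates side by side even without a test. Nothing else in the plan would warn them:
- The missing-data provisions in 9.3.4 cover the change scores and the longitudinal models, not this rate.
- The compliance rate in 9.2.2.3 leaves out patients whose forms are missing because of death, progression or early discontinuation.

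**Working it through.** **1. The plan's own figure behind unequal observation.** The documents give no figure for recovery, so the check starts from the PFS design in 9.3.2: medians 18 and 26 months, 255 patients per arm, accrual A = 42 months, analysis at T = 54 months. For hazard h, the expected event fraction is p = 1 − [exp(−h(T−A)) − exp(−hT)]/(hA).
- Control, h = ln2/18 = 0.0385: p ≈ 0.688.
- Ixazomib, h = ln2/26 = 0.0267: p ≈ 0.563.
- Events: 255 × (0.688 + 0.563) ≈ 319, as stated.
- Power = Φ(½√319 × |ln HR| − 1.96) = 0.890 at HR 0.70 and 0.907 at HR 18/26 = 0.692. The plan says approximately 90%.

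The PFS assumptions are reproduced. They are a design alternative, not an observed result.

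**2. Simulation with the same true recovery in both arms.** There were 200,000 patients per arm.
- From the documents: the form schedule in 6.3.2, including the discontinuation form and the four post-treatment forms, and PFS medians of 18 and 26 months.
- Assumed, identical in both arms: median time to worsening 6 to 48 months; median time to recovery 3 to 48 months; each form returned with probability 1, 0.8 or 0.6; 10% of PFS events are deaths; median survival after progression 40 months; no data cut-off.

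The 60% and 80% compliance in 9.3.4 refers to forms at both of two time points. If forms are independent, that is √0.6 ≈ 0.77 to √0.8 ≈ 0.89 per form, which the grid covers.

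**3. Results with no stopping for toxicity.**
- The crude recovery rate is 2.5 to 8.4 points higher on ixazomib (median 5.9). Without the post-treatment forms the range is 2.0 to 7.8 (median 4.7).
- Base case (worsening 24 months, recovery 12 months, all forms returned): +6.1 points.
- Patients with an observed drop and no later form: about 3 to 15%.
- With PFS equal in the arms, the difference is zero apart from simulation error.

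**4. Results when stopping differs (base case).**
- Control stops for toxicity at 0.01 per month. With ixazomib at 0.01, 0.02 and 0.03 per month, the difference is +5.2, +1.2 and −2.4 points.
- Extra stopping on ixazomib only after worsening, at 0.01, 0.02 and 0.04 per month: +4.1, +1.9 and −1.5 points.
- Break-even for time on treatment: ln2/18 − ln2/26 = 0.0118 per month, and 1 − exp(−12 × 0.0118) ≈ 13% per year.

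**5. Would a counting rule alone be enough?** No. With 60% form return, worsening at 24 months and recovery at 12 months, the crude rates are 49.1% and 56.8%, a gap of 7.7 points. Excluding patients with no later form still leaves a gap of 6.8 points. Most of the distortion comes from the amount of later observation.

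**6. Precision.** For 44 of 80 worsened patients recovered (55%), the exact 95% interval is 43.5% to 66.2%. For 82 of 150 it is 46.3% to 62.8%. These are about ±11 and ±8 points; the counts of 80 and 150 are assumed. The standard error of a between-arm difference is √(2 × 0.55 × 0.45/n), or 7.9 points at n = 80 and 5.7 at n = 150.

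**7. Does the proposed estimate remove the distortion?** With equal true recovery and PFS of 18 versus 26 months, the crude rates differed by +4.8 to +8.3 points over the settings rerun. Estimates of cumulative incidence at 6 and 12 months after first observed worsening differed by no more than about 2 points.

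**The case against.** The strongest reply is that the direction is not fixed. A reader might infer that follow-up will be longer on ixazomib, so that the endpoint builds in an advantage of several points for that arm. The documents do not support this. The 26-month median is a hypothesis. Section 9.3.2 expects moderately more toxicity on ixazomib, and the neuropathy rules in 5.5.3 can take a patient off treatment. Step 4 shows that such stopping can cancel or reverse the gap. This part of the objection stands.

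A reader might also infer that patients with no later form count as not recovered. The stated denominator makes that the natural reading, but the plan does not say it. Excluding them is also compatible with the text.

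It is fair, too, that the rate is descriptive. The two key secondary comparisons in 9.3.4 are time to worsening and time to improvement. The possible distortion is similar to or smaller than the standard error of a difference. Persistence of neuropathy is also visible in the scores at each form, the mixed models, and the PRO-CTCAE numbness and tingling items.

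These points limit the consequence but leave the defect. A rate that moves either way with progression and stopping cannot be read as recovery from neuropathy.

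**Conclusion.** The concern holds in a conditional form. The recovery rate is an untimed crude proportion with no rule for patients who lack a later form, and it depends on how long each patient is observed after worsening. With PFS of 18 versus 26 months and similar stopping for toxicity, equal true recovery looks about 2 to 8 points better on ixazomib. With equal time on treatment the distortion is zero. Extra stopping on ixazomib above roughly 0.012 per month can reverse it.

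The size rests on onset, recovery and stopping rates that the documents do not give. It also assumes that recovery does not depend on whether treatment has stopped. No single figure or fixed direction should be attached to the endpoint. The exact binomial interval covers sampling error only. The consequence is limited because no test depends on this rate, but the change is cheap and worth making.

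**What to change.** In 9.2.2.2 and 9.3.4, replace the proportion with the cumulative incidence of return to baseline, measured from the date of the first form showing an 8-point drop. Report it by arm, with confidence intervals, at fixed times such as 6 and 12 months. Censor at the last form and treat death as a competing event, saying which deaths after the last form count. Show by arm the number of worsened patients with no later form.

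The cost is SAP wording and one extra programmed estimate; no new data are needed. Because forms continue quarterly for a year after treatment stops, most patients who worsen on treatment remain scheduled for assessment across these windows. The small downside is a time-specific rate instead of one overall percentage. Censoring at the last form also assumes that patients who stop returning forms would recover like those who continue, and the SAP should state this.

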6.3.1 PRO Instruments

FACT

Health-related QOL will be assessed with three instruments: 1) the FACT-General (G) functional well-being (FWB) and physical well-being (PWB) subscales.³⁹ Each FACT-G subscale has 7 items. The 14 items are based on a 5-point Likert scale (0-4) resulting in a score ranging from 0 to 56 points with a higher score indicating better health-related QOL; 2) The FACT/GOG-Neurotoxicity Trial Outcomes Index (FACT/GOG-Ntx TOI) comprised of the FWB and PWB subscales plus the neurotoxicity subscale which has 11 items, summing to a score of 0-100;⁷⁰ and 3) the FACT-Multiple Myeloma Trial Outcomes Index (FACT-MM TOI) comprised of the FWB and PWB subscales plus the multiple myeloma subscale which has 14 items, summing to a score of 0-112 for the instrument.⁴⁰ The anticipated time to complete is roughly 8-10 minutes.

NCI PRO-CTCAE

NCI PRO-CTCAE items will be administered to allow patients to self-report symptomatic adverse events experienced on treatment. In its current version (dated 6/22/2018), there are 80 symptomatic AE terms included in the PRO-CTCAE item library which draw directly from the CTCAE, the standardized safety assessment lexicon for cancer clinical trials. Items correspond to 5 attributes measured [frequency (F), severity (S), interference (I), presence/absence (P) and amount (A)] based on multiple choice questions. Response for each attribute except P which is binary is on a 5-point Likert scale with 5 indicating 'almost constantly' frequency, 'very severe' severity, 'very much' amount or 'very much' interference. For each attribute, recall is the past 7 days. Attributes measured for each symptomatic AE varies and comprise the PRO-CTCAE item library.

For this study, 23 symptomatic AEs summing to 38 items have been selected as presented below. There are 10 symptomatic AEs which are assessed using one item, 11 symptomatic AEs which are assessed using two items, and 6 symptomatic AEs which are assessed using three items. The types of items in order of prevalence include severity (n=18 symptomatic AEs), interference (n=9 symptomatic AEs), frequency (n=7 symptomatic AEs), present/not present (n=4 symptomatic AE), and amount (none). The anticipated time to complete should be approximately 10 minutes.

PRO-CTCAE Symptomatic AE (Attributes)	CTCAE Term – System Organ Class
Dry Mouth (S)	Dry mouth - Gastrointestinal disorders
Taste Changes (S)	Dysgeusia - Nervous system disorders
Nausea (FS)	Nausea - Gastrointestinal disorders

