9.3.4 Patient-Reported Outcomes (PRO) Endpoints

PRO compliance and completion rates will be tabulated at each collection time point and overall separately for the FACT-G (FWB and PWB subscales), FACT-Ntx, FACT-MM, ASK-12 and PRO-CTCAE instruments.

Health-Related Quality of Life (QOL)

To assess the impact of treatment and disease on health-related QOL, there are two co-primary endpoints: change in FACT/GOG-Ntx TOI from baseline to end of cycle 12 post-randomization (beginning of cycle 13 assessment) and change in FACT-MM TOI from baseline to end of cycle 24 (beginning of cycle 25 assessment) post randomization. The FACT-G (FWB and PWB subscales), Ntx and MM will be administered at the beginning (day 1) of every 3 cycles for the first 24 cycles (beginning of cycles 4, 7, 10, 13, 16, 19, 22 and 25) and every 6 cycles thereafter (up to completion of 48 cycles of therapy (beginning of cycles 31, 37, 43, and 49), or at treatment discontinuation prior to completion of 48 cycles of therapy. During long-term follow-up/post-treatment end, there will be four quarterly assessments for 1 year. We hypothesize that treatment with ixazomib will not result in a significant difference in the FACT/GOG-Ntx TOI over the first 12 cycles and that improved PFS will result in higher FACT-MM TOI scores by end of 24 cycles. All patients who receive at least one dose of study drug and complete the QOL assessment at both time points are eligible. Power calculations are based on t-tests comparing the two treatment arms for the change in score with a 2-sided 0.05 alpha split between these comparisons. In an unselected group of MM patients being treated with oral therapy (n=118), the FACT-MM TOI had a standard deviation (SD) of approximately 21 points. The FACT-Ntx TOI has a reported SD of 14-16.⁷⁰ We propose using a general effect size measure of half standard deviation to establish the minimally important difference (MID).^{47,69} We therefore will establish a MID of 10 for the FACT-MM TOI and 8 for the FACT-Ntx TOI. We assume 90% and 81% of patients are alive by year 1 and 2, respectively, as well as a 10% drop-out rate resulting in potential patients of n=414 and n=373 for each analysis. Sensitivity for the proportion assumed to submit the questionnaire at both time points (compliance rates of 60% and 80%), allowing for a range of instrument variability and assuming different correlation (0.6, 0.4) between repeated measures was performed (Table 3). The difference in the FACT-Ntx TOI mean change score over 12 cycles of treatment between the ixazomib-lenalidomide arm and the placebo-lenalidomide arm that can be detected with 80% power at 2-sided 0.025 significance level ranges from 3.7-6.9 points as shown below. The difference in the FACT-MM TOI mean change score over 24 cycles of

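### Patients with a baseline FACT-MM TOI of 103 to 112 cannot have the 10-point improvement event, yet the plan keeps them in the time-to-improvement log-rank test and the response-rate denominator

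*Combined protocol and SAP*

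**What the plan says.** Section 6.3.1 builds the FACT-MM TOI from two 7-item well-being subscales and a 14-item myeloma subscale, "summing to a score of 0-112 for the instrument". It describes the well-being items as scored 0 to 4, with "a higher score indicating better health-related QOL". Section 9.3.4 sets the threshold: "We therefore will establish a MID of 10 for the FACT-MM TOI and 8 for the FACT-Ntx TOI".

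Two secondary endpoints in 9.2.2.2 use the 10-point threshold for improvement. One is time to improvement: "Time to improvement of the FACT-MM TOI defined as the time from baseline to an increase of 10 points (MID"), censored at the last assessment. The other is the response rate, "defined as the proportion of patients experiencing a MID improvement since baseline at each assessment time point". No confirmation at a second visit is required.

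Section 9.3.4 names time to improvement as one of two key secondary quality-of-life comparisons: "time to improvement of the FACT-MM TOI will be analyzed with the KM method and compared using the log-rank test". The significance level is also given there: "We will establish significance as alpha=1.67% based on Bonferroni adjustment (5% divided over 3 comparisons"). The response rate is reported for each arm with exact binomial 95% intervals and is not compared between arms.

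Neither section limits these analyses by baseline score. For the Ntx recovery rate, by contrast, 9.2.2.2 does confine the denominator to patients who can have the outcome, namely those who first worsened.

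**The concern.** A patient who starts within 10 points of the top of the scale cannot meet the definition of improvement, whatever the treatment does. Such patients add no events but remain at risk until censored. As the patients able to improve have their events, the later risk sets hold a growing proportion who cannot. If one arm improves faster, this happens sooner in that arm, and the later log-rank contributions then pull against it.

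High baselines are plausible here, although this is inference. Patients have ECOG status 0 to 2, are established on lenalidomide maintenance, and are excluded for grade 2 or higher neuropathy or diarrhea (Sections 3.1 and 3.2). What is at stake is the chance of detecting a real benefit on a key secondary endpoint tied directly to objective 2.4.2.2.

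**Working it through.** **Inputs from the documents.** Range 0 to 112, threshold +10, alpha 1.67% (sidedness not stated; two-sided assumed), 510 patients randomized 1:1, 10% drop-out. On spread, "the FACT-MM TOI had a standard deviation (SD) of approximately 21 points"; Table 3 uses SD 18 to 22 and correlation 0.4 to 0.6. The baseline mean and the share above 102 are not given, so both are varied as assumptions.

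**1. The plan's own figure.** No power is stated for time to improvement. The nearest figure is Table 3, for mean change. SD of change = SD × √(2(1 − ρ)); detectable difference = (z₀.₉₈₇₅ + z₀.₈₀) × SD of change × √(2/n).
- SD 18, ρ 0.6, n = 148: SD of change 16.1; difference 5.77, or 5.79 with the noncentral t. Stated: 5.8.
- SD 22, ρ 0.4, n = 112: SD of change 24.1; difference 9.93, or 9.99 with the noncentral t. Stated: 10.0.

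Table 3 reproduces. It does not use the 10-point event.

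**2. The limit.** (7 + 7 + 14) items × 4 = 112, and 112 − 10 = 102. A baseline of 102 can just reach the event; 103 to 112 cannot.

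**3. Share above 102.** Normal scores with SD 21, cut at 102.5. In each pair, the first figure truncates the distribution to 0–112 and the second does not.

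| Assumed mean | Share above 102 |
|---|---|
| 75 | 6.0% / 9.5% |
| 85 | 11.8% / 20.2% |
| 95 | 19.8% / 36.0% |

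**4. Log-rank power, constant hazards.** 458 patients, the protocol's visit grid to cycle 48, random censoring, 2,000 runs, and the same share unable to improve in both arms. Among patients able to improve, 30% or 50% of controls do so by month 24, with a rate ratio of 1.5 or 1.7. Cells show power with these patients kept / excluded.

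| Share | 30%, 1.5 | 30%, 1.7 | 50%, 1.5 | 50%, 1.7 | Gain (points) |
|---|---|---|---|---|---|
| 5% | 0.46 / 0.49 | 0.73 / 0.76 | 0.63 / 0.68 | 0.89 / 0.92 | 2–5 |
| 10% | 0.41 / 0.44 | 0.70 / 0.74 | 0.56 / 0.65 | 0.83 / 0.91 | 3–9 |
| 20% | 0.33 / 0.39 | 0.56 / 0.65 | 0.45 / 0.60 | 0.70 / 0.86 | 6–17 |
| 30% | 0.26 / 0.33 | 0.48 / 0.58 | 0.34 / 0.53 | 0.57 / 0.81 | 7–24 |

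Exclusion loses no events, because the excluded patients have none. Nor does it restore everything: at 30%, 50% improving and ratio 1.5, power with no such patients in the trial would be 0.72, against 0.53 after exclusion.

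**5. Log-rank power, simulated scores with an early effect.** Exchangeable normal scores, rounded and clipped to 0–112, Table 3's SDs and correlations, 150 per arm, 8 assessments, a +8 shift from the first assessment, no dropout. The low end of each range is SD 22 with correlation 0.4; the high end is SD 18 with correlation 0.6.

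| Mean | Share above 102 | All patients | Baseline ≤ 102 | Gain at low / high end |
|---|---|---|---|---|
| 75 | 6–11% | 46–91% | 70–98% | 24 / 7 |
| 85 | 16–21% | 22–77% | 67–97% | 45 / 20 |
| 95 | 34–37% | 7–32% | 52–90% | 45 / 58 |

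Type I error of the restricted test was 0.017 to 0.018 in this model, against a nominal 0.0167.

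**6. Same model, gradual effect.** A linear rise to +8, 8% dropout per visit, SD 20, correlation 0.6. All patients versus restricted: 15% vs 18% (mean 75), 10% vs 12% (mean 85), 6% vs 7% (mean 95). The gains are 3, 2 and 1 points.

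**7. Response rate.** Expected rate in all patients = (1 − share) × rate among those able to improve. With assumed rates of 30% and 45% and a share of 20%, these become 0.8 × 30 = 24% and 0.8 × 45 = 36%, so a 15-point difference reads as 12.

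**The case against.** Randomization balances the high-baseline patients, so the comparison is valid and favors neither arm. That stands: the effect is attenuation only.

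A reader might infer that power is sharply cut. The documents do not support that as a fact. They give an SD but no baseline mean or distribution, and the large losses in step 5 come from a demanding model. There the full shift is present at once, and 72–91% of control patients able to improve cross +10 by noise alone over eight visits. Section 9.3.4 instead expects higher scores to follow from better PFS by the end of 24 cycles, which is closer to step 6. Clipping at mean 95 also places 18–23% of patients at exactly 112, an artefact. Yet the loss does not vanish: with the early shift and 15% dropout per visit (mean 85, correlation 0.6), power is 62% for all patients against 88% restricted.

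A reader might also infer that the response-rate comparison loses power. None is planned. As a proportion of all patients the reported rate is a correct description; it is low only as a statement about those able to improve.

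Nor is this the main test of patient benefit from disease control. That is the co-primary mean change in FACT-MM TOI at 24 cycles, which has its own sensitivity analysis and planned mixed models and does not use the 10-point event.

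Lastly, restriction changes the population to which the result applies, and keeping all patients in the main analysis with a restricted sensitivity analysis is defensible. What favors restricting the main comparison is that it uses a pre-randomization value, loses no events, and was at least as powerful in every scenario examined.

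**Conclusion.** The point holds as a cheap improvement. That a baseline of 103 to 112 rules out the event, and that no at-risk rule is stated, follow from the documents alone. The size of the power loss does not. Under assumed means of 75 to 95 it runs from about 1–5 points (a share near 5%, or a gradual effect with dropout) to about 20–50 points (a share of about 20% or more with an early effect), with intermediate cases between. The 58-point gap at mean 95 is left out of that range because of the clipping artefact. These figures rest on two-sided alpha of 1.67%, normal or constant-hazard models, and equal shares in the two arms. Type I error is intact, no stated power figure is wrong, and for the response rate the only effect is dilution by (1 − share).

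**What to change.** In 9.2.2.2 and 9.3.4:
- run the time-to-improvement comparison in patients with baseline FACT-MM TOI of 102 or lower;
- report the number above 102 in each arm;
- give the all-patient log-rank result as a sensitivity analysis;
- report the response rate both for all patients and for those with baseline 102 or lower.

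This takes a few sentences and no new data. It should be written in before unblinded PRO results are seen. Pooled baseline scores, once available, would show the share above 102 without unblinding. The cost is that the main conclusion for this endpoint applies to patients with room to improve, which the report should say.
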